### 3.2.3 Tertiary Efficacy Outcome Measures

The following tertiary efficacy outcome measures apply to both the evaluable subset of the FAS as well as to the FAS:

- Serum PSA at each assessment, changes from baseline to each assessment, and percentage change from baseline of serum PSA at each assessment
- Subject reported QoL (EQ-5D-5L questionnaire) at each assessment and changes from baseline to each assessment
- CTCs at each assessment and changes from baseline to each assessment
- Impact of duration of prior CB on outcome (CB response at weeks 16 and/or 24, PFS, TTP, duration of response)
- Impact of time from diagnosis of metastases to study enrollment on outcome (CB response at weeks 16 and/or 24, PFS, TTP, duration of response)
- Tumor volume at each assessment and change from baseline to each assessment
- Plasma concentrations of GTx-024 and GTx-024 glucuronide on outcome (CB response at weeks 16 and/or 24)

### 3.2.4 Safety Outcome Measures

The following safety outcome measures apply to both the evaluable subset of the FAS as well as to all subjects enrolled and treated:

- AEs and concomitant medications
- Laboratory examinations (clinical chemistry, hematology, and urinalysis)
- Physical examinations
- Vital signs
- ECOG performance status
- ECG parameters

Protocol: A Phase 2 Open Label, Multi-Center, Multinational Study Investigating The Efficacy and Safety Of GTx-024 On Advanced, Androgen Receptor-Positive Triple Negative Breast Cancer (AR+ TNBC)	Compound No.: GTx-024 Author: [name]
---	---

### 3.2.5 Pharmacokinetic outcome measures

- Plasma concentrations of GTx-024 and GTx-024 glucuronide at each of the assessed time points

Protocol: A Phase 2 Open Label, Multi-Center, Multinational Study Investigating The Efficacy and Safety Of GTx-024 On Advanced, Androgen Receptor-Positive Triple Negative Breast Cancer (AR+ TNBC)	Compound No.: GTx-024 Author: [name]
---	---

## 4 STUDY DESIGN

This is an open label, multicenter, multinational Phase 2 study to assess the efficacy and safety of GTx-024 in female subjects with AR+ TNBC. Subjects will be administered GTx-024 18 mg given PO daily for up to 12 months. Simon's two-stage (optimal) design will be used to assess primary efficacy and will require up to 41 evaluable subjects; i.e., subjects with centrally confirmed AR+ who receive at least one dose of study drug.

In order to obtain these numbers of evaluable subjects, 21 to 55 subjects including over-enrollees, will be enrolled to receive a daily PO dose of GTx-024 18 mg. Fourteen of the aforementioned subjects may be over-enrolled to allow for replacement of subjects to account for lack of centrally confirmed AR+ status, or for the rare subject who is enrolled but does not receive study drug. Forty-one TNBC subjects with centrally confirmed AR+ who receive at least one dose of study medication (evaluable subjects) will be needed for primary analysis purposes, and will be included in the FAS. The trial will test for an unacceptably low CBR of  $\leq 5\%$  versus a CBR more consistent with  $\geq 20$ . The first stage will be assessed among the first 21 evaluable subjects. If at least 2/21 subjects achieve CB (defined as CR, PR, or SD) at week 16, the trial will proceed to the second stage of recruitment up to a total of 41 evaluable subjects. Otherwise the trial will be discontinued for lack of efficacy.

Subjects who are not confirmed AR+ may remain on the trial, but will not be part of the primary efficacy analysis – these subjects will contribute to secondary and tertiary analyses as noted below.

With the exception of elevated LFTs and hypercalcemia, both of which are further addressed below, subjects who experience an AE with Grade  $\geq 3$  intensity (National Cancer Institute-Common Terminology Criteria for Adverse Events [NCI-CTCAE], Version 4.0) and/or intolerance may have a dose reduction from 18 mg to 9 mg per day or a drug interruption based on the medical judgment of the Investigator and after confirmation by the study Medical Monitor. The drug interruption may last for a period of up to 7 days after which the subject must be rechallenged with study drug (18 mg or 9 mg) or discontinued from the study. In the case of a dose reduction, once the AE has resolved or reduced in intensity to Grade 1, the subject may be rechallenged with 18 mg or maintained at 9 mg at the discretion of the Investigator.

For  $\geq$  Grade 3 elevations in liver function tests, study drug should be held. A recheck of LFTs should be done within 48 hours. At the discretion of the investigator, study drug may be restarted at the 18mg dose or reduced to a 9mg dose when the LFTs have resolved to Grade 1 or better.

In the event of  $\geq$  Grade 2 hypercalcemia, study drug should be held until hypercalcemia resolves to Grade 1 or better.

Protocol: A Phase 2 Open Label, Multi-Center, Multinational Study Investigating The Efficacy and Safety Of GTx-024 On Advanced, Androgen Receptor-Positive Triple Negative Breast Cancer (AR+ TNBC)
	
Compound No.: GTx-024 Author: [name]

--	---

[figure not shown]
After randomization on Day 1, a safety check involving a comprehensive metabolic panel (Chem 14), including serum calcium and liver function tests, will be performed at Week 2 ( $\pm 3$  days). The week 2 safety check should include a clinic visit. The investigator may repeat these checks at Week 3 ( $\pm 3$  days) if clinically indicated.

In the event of hepatotoxicity, please also refer to [Section 9.4 Halting Rules](#).

The subjects who demonstrate CB will be treated for up to 12 months from the date of the first dose of study treatment (as long as they continue to demonstrate CB from the treatment during these 12 months). Subjects who continue to demonstrate a beneficial response from the study treatment at 12 months will be offered to continue in a safety extension study under a separate protocol. All subjects will be followed-up for one month after the last dose of GTx-024 is received, for safety purposes. Additionally, all subjects will be followed for vital status every 60 days post the discontinuation of study treatment for up to 24 months.

A flow chart of the study is shown in [Figure 1](#) below.

**Figure 1: Flow Chart of Study Plan**

Possible pause in enrollment: The implementation of Simon’s two-stage (optimal) design could cause a pause in enrollment of the trial prior to proceeding to the second stage. For example, if the required 21 evaluable subjects in the first stage of the trial are enrolled and 19 have either terminated the trial or been assessed as not achieving CBR at 16 weeks, it will be necessary to pause enrollment until the remaining two evaluable subjects are fully assessed for CBR, i.e., either withdraw prior to week 16 or have the week 16 RECIST 1.1 assessment.

Protocol: A Phase 2 Open Label, Multi-Center, Multinational Study Investigating The Efficacy and Safety Of GTx-024 On Advanced, Androgen Receptor-Positive Triple Negative Breast Cancer (AR+ TNBC)	Compound No.: GTx-024 Author: [name]
---	---

#### 4.1 Substudies (if applicable)

Not applicable.

#### 4.2 Safety Monitoring Committee (SMC)

In order to protect the safety of the subjects, a Safety Monitoring Committee (SMC) will be established for the study to review the safety data on an ongoing basis. The SMC will consist of, as a minimum, the Medical Monitor, Safety Reviewer with an oncology background, a statistician, and two GTx, Inc. representatives, consistent with the SMC charter.

The first safety review meeting will occur approximately one to two weeks following the enrollment of first 5 subjects in the study. Additionally, the SMC chairman or GTx, Inc. may call an unscheduled review of the study by the SMC if there is a concern for subject safety. Following the meetings, the SMC chairperson is responsible for communicating one of the following recommendations to GTx, Inc.:

- Continue the study without modification
- Continue the study with modifications (to be specified); or
- Stop the study due to safety (specific safety concern[s] to be specified)

Protocol: A Phase 2 Open Label, Multi-Center, Multinational Study Investigating The Efficacy and Safety Of GTx-024 On Advanced, Androgen Receptor-Positive Triple Negative Breast Cancer (AR+ TNBC)	Compound No.: GTx-024 Author: [name]
---	---

## 5 STUDY ENROLLMENT AND WITHDRAWAL

### 5.1 Subject Inclusion Criteria

**Subject Inclusion Criteria:** Subjects eligible for inclusion in this study must meet **all** of the following criteria:

1. Able and willing to give voluntary, written and signed, informed consent;
2. Women  $\geq$  18 years of age;
3. Women with TNBC who have received at least one but no more than two prior chemotherapy regimens for the treatment of advanced or metastatic TNBC;
4. Confirmation of AR+ (defined as  $\geq$  10% nuclear AR staining by immunohistochemistry [IHC]) TNBC in either the primary or metastatic lesion, assessed prior to the start of or during the screening period by a local laboratory or by medical history;
5. TNBC confirmed by medical history as: HER2-negative (confirmed by IHC 0, 1+ regardless of fluorescence in situ hybridization [FISH] ratio; IHC 2+ with FISH ratio lower than 2.0 or *HER2* gene copy less than 6.0; FISH ratio of 0, indicating gene deletion, when positive and negative in situ hybridization [ISH] controls are present); ER negative (confirmed as ER expression less than or equal to 1% positive tumor nuclei); progesterone receptor negative (confirmed as progesterone receptor expression less than or equal to 1% positive tumor nuclei);
6. Availability of paraffin embedded or formalin fixed tumor tissue; OR, a minimum of 10 and up to 20 slides of archived tumor tissue or new biopsy, if archived tissue is unavailable, for central laboratory confirmation of AR status and molecular subtyping. Metastatic tumor tissue is preferred when possible;
7. Subjects must have either measurable disease or bone-only non-measurable disease, according to RECIST 1.1;
8. Subjects with bone metastases should be treated with intravenous bisphosphonates or subcutaneous denosumab (or investigator preferred standard of care) prior to and/or during the trial, unless there is a contraindication or subject intolerance to these therapies. For subjects who are normocalcemic, therapy can be initiated at the time the subject initiates study drug;
9. Eastern Cooperative Oncology Group (ECOG) performance status 0 or 1 at the time of screening and enrollment;

Protocol: A Phase 2 Open Label, Multi-Center, Multinational Study Investigating The Efficacy and Safety Of GTx-024 On Advanced, Androgen Receptor-Positive Triple Negative Breast Cancer (AR+ TNBC)	Compound No.: GTx-024 Author: [name]
---	---

10. Negative serum pregnancy test in women of childbearing potential (premenopausal or less than 12 months of amenorrhea post-menopause, and who have not undergone surgical sterilization), no more than 7 days before the first dose of study treatment;
11. For women of childbearing potential who are sexually active, agreement to use a highly effective, non-hormonal form of contraception during and for at least 6 months after completion of study treatment; OR, a fertile male partner willing and able to use effective non-hormonal means of contraception (barrier method of contraception in conjunction with spermicidal jelly, or surgical sterilization) during and for at least 6 months after completion of study treatment;
12. Adequate organ function as shown by:
  - Absolute neutrophil count  $\geq 1,000$  cells/mm^3
  - Platelet count  $\geq 100,000$  cells/mm^3
  - Hemoglobin  $\geq 9$  g/dL
  - Serum aspartate aminotransferase (AST) and ALT  $\leq 2.5$  ULN (or  $\leq 5$  if hepatic metastases are present)
  - Total serum bilirubin  $\leq 2.0 \times$  ULN (unless the subject has documented Gilbert Syndrome)
  - Alkaline phosphatase levels  $\leq 2.5 \times$  ULN ( $\leq 5 \times$  ULN in subjects with liver metastasis)
  - Serum creatinine  $\leq 2.0$  mg/dL or 177  $\mu$ mol/L
  - International normalized ratio (INR) or activated partial thromboplastin time (aPTT)  $< 1.5 \times$  ULN (unless on anticoagulant treatment at screening);
13. Able to swallow capsules;
14. Any toxicity from prior chemotherapy has resolved or is Grade 1 (NCI-CTCAE, Version 4.0).

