 Urine pregnancy tests will be done at the site with a pregnancy stick test in premenopausal patients. Postmenopausal patients are exempt from monthly urine pregnancy test.

 First dose to be given at site during this visit.

 A comprehensive metabolic panel (Chem 14), including serum calcium and liver function tests, will be performed at Week 2 ( $\pm 3$  days).

Abbreviations: AR = Androgen Receptor, BC = Breast Cancer, CR = complete response, CT = Computerized Tomography, CTCs = circulating tumor cells, ECG = Electrocardiogram, ECOG = Eastern Cooperative Oncology Group, eCRF = electronic case report form, EOT = End of Treatment, ER = Estrogen Receptor, FU = Follow-up, HBsAg = Hepatitis B surface Antigen, HBV = hepatitis B virus, HCV = hepatitis C virus, HER2 = Human Epidermal Growth Factor Receptor 2, HIV = Human Immunodeficiency Virus, ICF = Informed Consent Form, IHC = Immunohistochemistry, MRI = Magnetic Resonance Imaging, PR = partial response, QoL = Quality of Life, PSA = Prostate Specific Antigen, V = Visit.

Protocol: A Phase 2 Open Label, Multi-Center, Multinational Study Investigating The Efficacy and Safety Of GTx-024 On Advanced, Androgen Receptor-Positive Triple Negative Breast Cancer (AR+ TNBC)

Compound No.: GTx-024  
Author: [name]

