observed in subjects with elevated ALT levels. Consistent with the effects of other orally administered anabolic agents, GTx-024 causes a dose dependent reduction in high-density lipoprotein (HDL), the clinical significance of which is unknown at this time. The proposed mechanism for reduction in HDL is due to stimulation of reverse cholesterol transport and increased HDL catabolism by hepatic lipase. Reductions in HDL are temporary and typically return to baseline 12 months after treatment initiation.

There were no other consistent, clinically relevant, dose-related effects of GTx-024 on ECGs or vital signs measurements (blood pressure or heart rate).

Investigators should be aware that blood levels of the tumor marker, CA27.29, have been shown to be modulated by compounds with androgenic activity as a result of the marker binding to the androgen regulated protein MUC-1. As a result, administration of GTx-024 has the potential to result in increases in CA27.29 that are not necessarily reflective of disease progression.

The drug used in this research study may affect a fetus. Subjects should not become pregnant nor breastfeed a baby while participating in this research study. Counselling about preventing pregnancy will be provided, if necessary, to study participants.

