## 7.2 Baseline

The following tests and procedures will be performed during the baseline visit (Visit 2), or results checked and confirmed:

- Eligibility criteria checked
- Review of prior/concomitant medications, including previous and current anticancer treatment
- Vital signs (heart rate, respiratory rate, temperature, blood pressure in a sitting position), if not done within the last 7 days
- ECOG performance status, if not done within the last 7 days
- Blood sampling for: hematology, biochemistry, and PSA if not done within the last 7 days; and serum lipid profile, serum hormones, and CTCs (enumeration and gene expression)
- Urine analysis, if clinically indicated
- AE collection
- Subjects will be asked to complete a QoL questionnaire
- Urine pregnancy test for premenopausal subjects (will be done at the site with a pregnancy stick test)
- First dose to subject at this visit. Subject will be given a carton box of 10 blister cards containing GTx-024
- Blood sample for pharmacokinetic assessment. The baseline blood sample should be collected before the subject is given their first dose of GTx-024. The exact time (hh:mm)

Protocol: A Phase 2 Open Label, Multi-Center, Multinational Study Investigating The Efficacy and Safety Of GTx-024 On Advanced, Androgen Receptor-Positive Triple Negative Breast Cancer (AR+ TNBC)	Compound No.: GTx-024 Author: [name]
---	---

and date of the blood sample will be recorded on the eCRF.

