### 7.3 Treatment Phase

The first dose of study drug will be administered at baseline (Visit 2). GTx-024 will be administered for up to 12 months from the first dose of treatment or until disease progression (whichever is sooner), subject's withdrawal of consent, or intolerability. Subjects who benefit from the treatment at week 16 and still benefit from the treatment at week 24 may continue to receive GTx-024 for a total of 12 months from the date of the first dose of study treatment (as long as they still benefit from the treatment during these 12 months). Subjects who continue to demonstrate a beneficial response at 12 months will be offered to continue in a safety extension study under a separate protocol.

After randomization on Day 1, a safety check involving a comprehensive metabolic panel (Chem 14), including serum calcium and liver function tests, will be performed at Week 2 ( $\pm 3$  days). The Week 2 safety check should include a clinic visit. The investigator may repeat these checks at Week 3 ( $\pm 3$  days) if clinically indicated.

During the first 4 months of the treatment phase, the subjects will be asked to come for a visit every 4 weeks (Visits 3, 4, 5, and 6), and then every 8 weeks (Visit 8 and Visits 10–12 as required if still on treatment). Visits 7 and 9 at weeks 20 and 28 will only take place in subjects who have CR or PR at Visit 6 (week 16) or Visit 8 (week 24), respectively (see below).

The following tests and procedures will be performed during Visits 3, 4, 5, 6, and 8 in the treatment phase:

- Review concomitant medications
- Physical examination, including weight and vital signs (heart rate, respiratory rate, body temperature, blood pressure in a sitting position)
- ECOG performance status
- Blood sampling for: hematology, biochemistry, serum lipid profile, coagulation status, serum hormones, and PSA
- Urine analysis, only if clinically indicated
- Urine pregnancy test for premenopausal subjects (at the site)
- AE collection
- Subjects will be asked to complete a QoL questionnaire
- GTx-024 drug accountability/dispensation

Radiologic assessments for anti-tumor effect will be done every 8 weeks whilst subjects receive treatment (Visit 4, Visit 6, Visit 8, and thereafter). In addition, if a subject has CR or PR at Visit 6 (week 16) or Visit 8 (Week 24), in compliance with RECIST 1.1 guidelines, a confirmation of the CR or PR should be done 4 weeks later (i.e., Visit 7 and/or Visit 9, as

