**Table 1: Clinical Laboratory Tests**

Hematology	Serum Chemistry (Chem 14)

 
• Hemoglobin
 
• Hematocrit
 
• Total and differential leukocyte count
 
• RBC count
 
• Platelet count
 
	
 
• Blood Urea Nitrogen
 
• Bilirubin (total and direct)
 
• Alkaline phosphatase
 
• AST
 
• ALT
 
• Albumin
 
• Sodium
 
• Potassium
 
• Creatinine
 
• Calcium
 
• Total globulin
 
• Total protein
 
• Glucose
 
• Chloride
 
• Total Carbon dioxide
 

Urinalysis	Additional Tests

 
• pH
 
• Specific gravity
 
• Protein*
 
• Glucose
 
• Ketones
 
• Bilirubin
 
• Blood*
 
• Nitrite*
 
• Urobilinogen
 
• Leukocyte esterase*
 
	
 
• HIV test
 
• HBsAg
 
• HCV
 
• Serum lipid panel
 
• Coagulation tests (INR, aPTT)
 
• Serum pregnancy test
 
• Urine pregnancy test (premenopausal subjects)
 
• PSA
 
• AR status of the tumor
 
• CTCs
 
• Blood hormone levels, including testosterone, estradiol, SHBG
 

* If urinalysis is positive for protein, blood, nitrite, and/or leukocyte esterase, a microscopic examination (for RBC, WBC, bacteria, casts, and epithelial cells) will be performed.
	

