-  In compliance with RECIST 1.1 guidelines, subjects who have CR or PR at week 16 and/or week 24 require confirmation within a month as follows:
- For subjects with measurable lesions, subjects will undergo CT/MRI based on the Investigator's medical judgment
-  Bone scans will be performed at screening and then at weeks 8, 16, and 24 in only those subjects with baseline bone metastases, or if clinically indicated.
-  In compliance with RECIST 1.1 guidelines, subjects who have CR or PR at week 16 and/or week 24 require confirmation within a month as follows:
- For subjects with non-measurable lesions, subjects will undergo X-ray or bone-scanning based on the Investigator's medical judgment and location of disease.
-  Blood sampling for pharmacokinetic assessment. The exact time (hh:mm) and date of the blood sample should be recorded on the eCRF. At the baseline visit, the blood sample should be collected before the subject is given their first dose of GTx-024. At visits 3 (week 4), 5 (week 12), 6 (week 16), and 8 (week 24), the date and approximate time of the last dose of GTx-024 prior to the blood sample should also be recorded; i.e., it should be documented whether the subject took the previous dose that morning or the evening before.
-  Urine pregnancy tests will be done at the site with a pregnancy stick test in premenopausal patients. Postmenopausal patients are exempt from monthly urine pregnancy test.
-  First dose to be given at site during this visit.
-  A comprehensive metabolic panel (Chem 14), including serum calcium and liver function tests, will be performed at Week 2 ( $\pm 3$  days).

Abbreviations: AR = Androgen Receptor, BC = Breast Cancer, CR = complete response, CT = Computerized Tomography, CTCs, circulating tumor cells, ECG = Electrocardiogram, ECOG = Eastern Cooperative Oncology Group, eCRF = electronic case report form, EOT = End of Treatment, ER = Estrogen Receptor, FU = Follow-up, HBsAg = Hepatitis B surface Antigen, HBV = hepatitis B virus, HCV = hepatitis C virus, HER2 = Human Epidermal Growth Factor Receptor 2, HIV = Human Immunodeficiency Virus, ICF = Informed Consent Form, IHC = Immunohistochemistry, MRI = Magnetic Resonance Imaging, PR = partial response, QoL = Quality of Life, PSA = Prostate Specific Antigen, V = Visit.

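### Women under 12 months of amenorrhea count as of childbearing potential at entry, but the scheduled pregnancy tests from Visit 2 on are written for premenopausal subjects only

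*Combined protocol and SAP*

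**What the plan says.** Section 5.1, criterion 10 (repeated in the Protocol Summary), asks for a "Negative serum pregnancy test in women of childbearing potential (premenopausal or less than 12 months of amenorrhea post-menopause", provided the woman is not surgically sterilized. The test must fall within the 7 days before first dose. Criterion 11 builds on the same definition: "For women of childbearing potential who are sexually active, agreement to use a highly effective, non-hormonal form of contraception", during treatment and for at least 6 months afterwards, with a partner-based alternative.

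After entry the wording changes. Section 7.2 has "Urine pregnancy test for premenopausal subjects (will be done at the site with a pregnancy stick test"). Section 7.3 has "Urine pregnancy test for premenopausal subjects (at the site"), and Sections 7.4 and 7.5 repeat this for the end-of-treatment and follow-up visits. Table 1 lists "Urine pregnancy test (premenopausal subjects"). In both schedules the urine-test row, which also covers Visits 10 to 12, carries footnote 12: "Urine pregnancy tests will be done at the site with a pregnancy stick test in premenopausal patients". The footnote then adds: "Postmenopausal patients are exempt from monthly urine pregnancy test". The only serum pregnancy test in the schedule is at screening.

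On risk, Section 2.3.1 states: "The drug used in this research study may affect a fetus".

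**The concern.** The eligibility section and the testing sections use different populations. A non-sterilized woman with, say, six months of amenorrhea who is regarded as post-menopausal must have a negative serum test to enter and must use contraception if sexually active, because the protocol considers her able to conceive. Yet no later test instruction names her, and the footnote appears to exempt her.

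What is at stake is fetal and patient safety. Under Section 9.2.4 a pregnant subject must stop the drug, but that rule can act only once the pregnancy is known. A woman who already has amenorrhea has no missed period to prompt suspicion. For premenopausal women the protocol did not rely on the entry test and contraception alone; it added urine tests through treatment and follow-up. It gives no reason for leaving them out for the other group that it places in the same category.

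**Working it through.** This is a consistency check between sections; the plan gives no figure to reproduce.

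**Step 1: groups and instructions side by side** (women not surgically sterilized)

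| Group | Entry serum test (criterion 10) | Contraception if sexually active (criterion 11) | Urine tests from Visit 2 (Sections 7.2 to 7.5, Table 1, footnote 12) |
|---|---|---|---|
| Premenopausal | Yes | Yes | Yes |
| Post-menopause, under 12 months of amenorrhea | Yes | Yes | Not named; exempt if footnote 12 is read literally |
| Post-menopause, 12 months or more | No | No | Exempt |

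The middle row is the gap. As written, it contains no scheduled pregnancy test after entry.

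**Step 2: can the terms be read so that the gap closes?** Neither premenopausal nor postmenopausal is defined in the document. There are two ways to try.

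- Carry the 12-month line of criterion 10 into footnote 12, so that a woman below it is not yet postmenopausal. This removes the exemption, but the positive instructions still name only premenopausal subjects.
- Read premenopausal as covering every woman under 12 months of amenorrhea. She would then be tested, but the second limb of criterion 10 would be redundant. That criterion joins the two groups with an *or* and calls the second one post-menopause.

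A site could adopt either reading. The text does not direct it to.

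**Step 3: how long the gap lasts.** It ends when she reaches 12 months of amenorrhea and leaves the category, or when menses resume and she is tested as premenopausal. Measured from first dose it lasts 12 months minus her amenorrhea at that time, so always less than 12 months.

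**Step 4: upper bound on the cost of closing it.** The urine-test row marks Visit 2 (1 test), Visits 3, 4, 5, 6 and 8 (5), Visits 10 to 12 (3), end of treatment (1) and follow-up (1):

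1 + 5 + 3 + 1 + 1 = 11 tests.

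All 11 can fall inside the gap only at the extreme of the visit windows:

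- Visit 12 is nominally at week 48, which is 48 × 7 = day 336. With the 7-day window the earliest is 336 − 7 = day 329.
- Take last dose and end-of-treatment visit on day 330. Follow-up is 28 ± 2 days after last dose, so the earliest is 330 + 26 = day 356.
- 52 weeks is 52 × 7 = 364 days, and 364 − 356 = 8 days.

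The woman would need less than about 8 days of amenorrhea at first dose, and it is hard to see why a site would call her post-menopausal. Eleven is therefore a ceiling, and the usual count would be lower.

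**The case against.** The strongest reply is that the terms are undefined and that the only line the protocol draws is 12 months of amenorrhea. A sensible investigator would apply that line and keep testing. This is fair, and it is why the documents do not support the stronger reading, which a reader might infer, that these women will in fact go untested. They show only that no scheduled test is clearly assigned to them. The reply does not remove the point. In a multinational, multicenter study a fetal-safety procedure should not depend on how each site reads an undefined word, and criterion 10 itself uses post-menopause for women below the 12-month line.

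The second reply is that protection already exists: the negative serum test shortly before first dose, contraception if sexually active, and counselling where needed (Section 2.3.1). Section 8.2.1 also lets the investigator order laboratory safety tests at unscheduled times, and Section 7.7 provides an eCRF page for the results. All of this stands and lowers the risk. Discretionary testing still depends on someone thinking of it. The 8-weekly imaging and the physical examinations might reveal a pregnancy, but neither is a pregnancy test: the imaging is for tumor response, and Section 8.1 describes the examination as height, weight, vital signs and ECOG status.

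The third reply is that the group may be empty. That also stands. Adult women of any menopausal status are eligible, so such a subject is possible, but the documents give no count and none should be supplied for them.

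**Conclusion.** The point holds as a wording conflict with a safety consequence. The protocol classes non-sterilized women with less than 12 months of amenorrhea post-menopause as able to conceive, then writes every scheduled test after entry for a narrower group. Read as written, they have zero scheduled pregnancy tests after the entry serum test for as long as they remain in the category, which is less than 12 months from first dose.

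The conclusion rests on the ordinary sense of premenopausal and on criterion 10 treating the two groups as distinct. Some sites may already test these women, the mitigations are real, and the number affected is unknown and may be zero. The two-stage design, the primary endpoint, alpha and power are untouched. The change is worth making because it is cheap and concerns fetal exposure, not because the trial's conclusions depend on it.

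**What to change.** In Sections 7.2, 7.3, 7.4 and 7.5, in Table 1, and in footnote 12 of both schedules (Protocol Summary and Appendix A), replace *premenopausal* with *women of childbearing potential (as defined in inclusion criterion 10)*. In footnote 12, limit the exemption to women with at least 12 months of amenorrhea or surgical sterilization.

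The cost is one term changed in these places, plus a urine stick at visits that already take place: at most about 11 per affected woman, so at most about 11 times however many such women enroll. No visit or blood draw is added, and the analysis does not change.
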